10.7 Subject Cost and Compensation

Subjects will not need to pay for any of the protocol-driven visits, procedures, or materials during the course of this study.

10.8 Research-Related Injury

If the subject is injured as a result of her participation in this study, the subject will be treated appropriately until resolution or stabilization of the injury. If it is determined that the Sonata treatment is responsible for physical injury to the subject, the sponsor will cover the cost of treatment for the injury, provided that the Sonata treatment was performed according to accepted medical practice and in accordance with the study protocol, the Instructions for Use, and other instructions provided by the sponsor, and to the extent that such costs are not covered by the subject's health insurance policy. The sponsor will not cover non-medical expenses and will not pay any compensation other than that which national laws may require.

10.9 Contact for Follow-up and Loss to Follow-up

Follow-up visits should be scheduled when the subject is present for the preceding visit. The Investigational Site may utilize postal mail, e-mail, and/or phone calls to send visit reminders.

Subjects who miss a study visit should be contacted immediately by the Investigational Site to determine the reason for the missed visit and to reschedule the visit as soon as possible to meet the study visit window. If the subject cannot be located after 5 attempts through a variety of communication modes (phone, email, letter), then the subject will be considered lost to follow-up. The Investigational Sites should collect multiple contact information (home phone, cell phone, work phone, email, home address, etc.) from the subject in order to minimize loss to follow-up. All attempts to contact the subjects will be documented and retained in the subject study record.

11 STUDY INVESTIGATORS

11.1 Investigational Sites

Up to 27 investigational sites may participate in this study in the United States, Europe, and Mexico.

11.2 Investigator Selection

- A. To qualify for participation in this study, investigators will have performed open and minimally invasive gynecologic procedures involving ultrasound, hysteroscopic surgery and electrosurgery, and have extensive experience to safely manage both anticipated and unanticipated operative and investigational occurrences.
- B. Selection criteria will include
 - 1) Experience with hysteroscopic and/or laparoscopic surgery and electrosurgery
 - 2) General proficiency with ultrasound

- 3) Access to a fibroid / HMB patient population that is sufficient to meet enrollment goals
 - 4) Study coordinator/research coordinator with sufficient time to dedicate to study
 - 5) Adequate facilities to reprocess the Sonata IUUS Probe according to the Instructions for Use
 - 6) Access to MRI
 - 7) Willingness to comply with all study requirements imposed by the protocol, Investigator Agreement, IRB / EC or equivalent review board, and local Ministry of Health regulations as applicable
 - 8) Not participating in a competing study
 - 9) Not on the FDA debarment list or otherwise restricted or disqualified as a clinical investigator by the FDA
- C. Selected investigators will include a mix of academic and community or private physicians who meet the required qualifications above.

11.3 Investigator Training

Investigators will undergo a hands-on training program prior to performing their first Sonata treatment. The record of complete training will be signed by the trainer and the Investigator prior to performance of any treatment. Initial treatments will be supervised by the Gynesonics case support team.

11.4 Investigator Discontinuation

Prior to participation in the study, all investigators must sign the Investigator Agreement, which outlines the Investigator's obligations in the study. The sponsor may elect to discontinue, or suspend, the Investigator's participation in the study due to poor study compliance, lack of compliance with applicable regulations or IRB/EC requirements, or insufficient recruitment of study subjects.

12 STUDY FLOW AND VISIT SCHEDULE

The study will be conducted in three phases as discussed below and depicted in Figure 1.

Consent

1. Screening and baseline phase
2. Treatment phase
3. Follow-up phase

Each of these phases is discussed separately below, following Table 3 Schedule of Screening Assessments and Table 4 Schedule of Study Assessments.

Overall study duration (first subject enrolled through last subject exit) will be comprised of approximately 22 months of subject enrollment and 36 months of follow-up post-treatment for a total duration of up to 58 months.

Study duration for an individual subject, once consented, will be up to 3 months for screening (including baseline measurements) and 36 months for follow up for a total duration of approximately 38-39 months.

Figure 1 Study Flow

[figure not shown]

Table 3 Schedule of Screening Assessments

ASSESSMENT	Timing of Assessment Prior to Enrollment				Immediately prior to Treatment
	Any time	Within 3 years	Within 12 Months	Within 3 Months	
Demographics	X				
Medical / Surgical History				X	
Pelvic / Menstrual History (at least last 3 months, but 6 months is preferable)				X	
Pelvic / Menstrual Pain - Numeric Rating Scale (NRS-11)				X	
Menstrual Diary (Pictorial blood loss assessment chart or "PBAC")				X	
Vital signs (temperature, pulse, blood pressure, height, weight)				X	
Pelvic Exam				X	
Cervical cancer screening (per subject history with adherence to national guidelines)		X			
Endometrial biopsy			X		
TVUS (SIS or hysteroscopy is optional for further assessment of the endometrial cavity)				X	
Hemoglobin level				X	
Serum creatinine			X		
Hemostasis assessment			X		
Urine or serum hCG				X	X
Cervical GC and chlamydia testing				X	
ce-MRI (screen MRI). MRI's will be forwarded to a central reader.				X	
UFS-QOL, EQ-5D, and WPAI:SHP Questionnaires				X	
Birth control assessment			Ongoing		
Concomitant medications			Ongoing		
Adverse events			Ongoing		
Final eligibility assessment					X

Table 4 Schedule of Study Assessments

Assessment	Baseline [Screening assessment]	Day 0 Treatment	FU Visit 1 10 day	FU Visit 2 30 day	FU Visit 3 3 mo	FU Visit 4 6 mo	FU Visit 5 12 mo	FU Visit 6 2 year	FU Visit 7 3 year
PBAC	[Screening assessment]				X	X	X		
UFS-QOL, EQ-5D, and WPAI:SHIP Questionnaires	[Screening assessment]				X	X	X	X	X
Vital signs as per screening		X							
Urine/serum hCG, (<24 hours pre-procedure)		X							
Venous thromboembolism risk classification		X							
Birth control adherence		X	X	X	X	X	X		
Sonata Treatment & Procedure Assessments Procedure & discharge times, pain VAS & tolerance, anesthesia and concomitant medications		X							
Adverse events		X	X	X	X	X	X	X	X
Concomitant medications		X	X	X	X	X	X		
ce-MRI	[Screening assessment]						X		
Return to normal daily activity**				X					
Post-procedure follow up Update to medical history and symptoms			X	X	X	X	X		
Pregnancy /pregnancy outcome				X	X	X	X	X	X
OTE and Subject satisfaction						X	X	X	X
Surgical Reintervention*						X	X	X	X

* if subject undergoes hysterectomy, operative and pathology reports shall be forwarded to study sponsor

**Subjects who are not back to normal activity will be followed weekly by phone until normal activity has resumed or is not expected to change

12.1 Screening / Baseline Phase

A. Candidate Identification

All patients at the Investigational Sites with a complaint of HMB will be asked about their interest in study participation. For those patients who express an interest to participate, the inclusion/exclusion criteria will be reviewed against existing medical history and the results of any standard clinical work-up to assess preliminary eligibility. Additionally, subjects may be recruited from site catchment area.

If the patient is not excluded on the basis of existing medical history and standard clinical work-up, the patient will be asked to provide informed consent to participate in the study. Before being asked to sign the informed consent form, patients will be given adequate time to consider the potential risks and benefits of study participation, as well as the study's follow-up schedule of 36 months and study requirements to complete various questionnaires and undergo various evaluations. If the patient understands the risks and benefits, and still wishes to participate, she will be asked to sign the informed consent form.

B. Final Screening/Baseline Assessments

Screening assessments include the following as shown in Table 3

- Demographics
- Medical / surgical history, including pregnancy history (prior pregnancies, live birth, c-section) and previous fibroid treatment (surgery, UAE, MRgFUS, GnRH-a, SPRM)
- Interview regarding hemostasis and menstrual history
- Vital signs (including temperature, pulse, blood pressure, height, weight), pelvic exam, and cervical cancer evaluation
- Endometrial biopsy
- Transvaginal ultrasound (TVUS)
- Saline-infused sonohysterography (SIS) or hysteroscopy is optional for further assessment of the endometrial cavity if needed to assess suspicion of intracavitary mass or significant intrauterine synechiae.
- Blood test (hemoglobin, serum creatinine)
- Cervical gonorrhea (GC) and chlamydia testing
- Urine or serum hCG
- UFS-QOL Questionnaire - to be completed with consideration to symptoms experienced during the last three menstrual cycles.
- EQ-5D Questionnaire - to be completed with consideration to symptoms experienced during the first full day of bleeding during the menstrual cycle in which the subject completes the Menstrual diary (PBAC).

- WPAI :SHP Questionnaire – to be completed with consideration to symptoms experienced during the last 28 days (most recent menstrual cycle)
 - Concomitant medications
 - ce-MRI. All MRI's will be forwarded to a central reader (core lab).
 - Menstrual diary (PBAC); Completion instructions will note that only the sanitary products provided should be used during the study while completing the PBAC.
- C. Each site will maintain a screening log noting the reasons for screening failures, including reasons for refusal to consent.
- D. At the time a subject initiates the screening process, she will be given a "Screening Kit" with tote bag, which will be comprised of the following:
- Menstrual diary (PBAC) and instructions
 - EQ-5D Questionnaire
 - A supply of sanitary products in sufficient quantity to cover use for one menstrual cycle while completing the PBAC.
- E. Subjects will be required to use catamenial products (sanitary pads and/or tampons) provided by the study sponsor for the screening and all subsequent study PBAC assessments.
- F. Subjects will be asked at each visit that requires completion of the PBAC whether they have used any non-study provided catamenial products during the time of the assessment. If the proper catamenial products were not used, the subject will be asked to complete a replacement PBAC during her next cycle.

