Subjects will be asked if they have undergone any surgical procedure to treat their heavy menstrual bleeding. If so, the procedure performed and the date of the reintervention will be recorded.

(d) Concomitant Medications

Subjects will be asked about concomitant medications, noting in particular concomitant medications taken for the treatment of HMB.

(e) Pregnancy/Pregnancy Outcomes

Subjects will be asked if they have become pregnant since the last follow-up visit. If so, the subject will be released from all protocol specified follow-up assessments and visits, however the subject will be followed and pregnancy outcomes (including any complications) will be recorded as described in Section 10.6 of this protocol.

(f) Post-treatment follow up

Subjects will be asked whether there is any change to their medical status. Subjects will be asked specifically if they have experienced any signs or symptoms of fibroid shedding: cramping, bleeding, passage of any tissue per vaginam.

(g) Adherence with/Continuance of Birth Control Method

Subjects will be asked if they are adhering to their chosen method of birth control, and if there have been any changes in their birth control method, including changes to medication type and preparation.

Note: During follow-up visit #2, the subject will be given study materials in anticipation of follow-up visit #3, which will be comprised of the following:

- a copy of the EQ-5D Questionnaire (Appendix A). The EQ-5D should be completed during the subject's 3rd menstrual cycle post-treatment, preferably on the first full day of bleeding. It should be completed based solely on symptoms from that cycle.
- Menstrual diary (PBAC) with completion instructions noting that only the sanitary products provided should be used during the study while completing the PBAC.
- A supply of sanitary products in sufficient quantity to cover use for one menstrual cycle for the completion of the PBAC.

3) Follow-up Visit #3: 3 Months (\pm 2 weeks)

(a) UFS-QOL, EQ-5D, and WPAI:SHP Questionnaires

Subjects will be asked to return their completed EQ-5D questionnaire and will be asked to complete the UFS-QOL and WPAI:SHP questionnaires.

(b) Menstrual Diary

Subjects will be asked to return their completed menstrual diary (PBAC) for the menstrual cycle preceding the visit.

(c) Adverse Events

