Subjects will be asked if they have experienced any untoward medical occurrences since the Sonata treatment. If so, these events will be recorded on the Adverse Event case report form, in accordance with the procedures outlined later in this protocol.

(d) Surgical Reintervention

Subjects will be asked if they have undergone any surgical procedure to treat their heavy menstrual bleeding. If so, the procedure performed and the date of the reintervention will be recorded.

(e) Pregnancy/Pregnancy Outcomes

Subjects will be asked if they have become pregnant since the last follow-up visit. If so, the subject will be released from all protocol specified follow-up assessments and visits, however the subject will be followed and pregnancy outcomes (including any complications) will be recorded as described in Section 10.6 of this protocol.

- (f) Amenorrhea
If the subject becomes amenorrheic, a pregnancy test (urine or serum hCG) will be performed and, if negative, a serum FSH level determination will also be obtained
- (g) Concomitant Medications
Subjects will also be asked about concomitant medications, noting concomitant medications taken for the treatment of excessive uterine bleeding.
- (h) Post-treatment follow up
Subjects will be asked whether there is any change to their medical status. Subjects will be asked specifically if they have experienced any signs of fibroid shedding: cramping, bleeding, passage of any tissue per vaginam.
- (i) Adherence with/Continuance of Birth Control Method
Subjects will be asked if they are adhering to their chosen method of birth control, and if there have been any changes in their birth control method, including changes to medication type and preparation.

Note: During follow-up visit #3, the subject will be given study materials in anticipation of follow-up visit #4, which will be comprised of the following:

- A copy of the EQ-5D Questionnaire (Appendix A). The EQ-5D should be completed during the subject's 6th menstrual cycle post-treatment, preferably on the first full day of bleeding. It should be completed based solely on symptoms from that cycle. If the subject has become amenorrheic, the EQ-5D may be completed at any time during the follow-up visit window.
- Menstrual diary (PBAC) with completion instructions noting that only the sanitary products provided should be used during the study while completing the PBAC.

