Subjects will be asked to indicate whether their uterine fibroid symptoms have improved, remained the same, or worsened. If the subject indicates that her symptoms have improved, she will be asked to rate the degree of improvement on a 7-point scale from “almost the same, hardly better at all” (1) to “a very great deal better” (7). If the subject indicates that her symptoms worsened, she will be asked to rate the degree of worsening on a 7-point scale from “almost the same, hardly worse at all” (-1) to “A very great deal worse” (-7).

(l) Adherence with/Continuance of Birth Control Method

Subjects will be asked if they are adhering to their chosen method of birth control, and if there have been any changes in their birth control method, including changes to medication type and preparation.

Note: During follow-up visit #4, the subject will be given study materials in anticipation of follow-up visit #5, which will be comprised of the following:

- A copy of the EQ-5D Questionnaire (Appendix A). The EQ-5D should be completed during the subject’s 12th menstrual cycle post-treatment, preferably on the first full day of bleeding. It should be completed based solely on symptoms from that cycle. If the subject has become amenorrheic, the EQ-5D may be completed at any time during the follow-up visit window.
- Menstrual diary (PBAC) with completion instructions noting that only the sanitary products provided should be used during the study while completing the PBAC.
- A supply of sanitary products in sufficient quantity to cover use for one menstrual cycle for the completion of the PBAC.

- 5) Follow-up Visit 6 and 7: 2 and 3 years
(Phone Call or mail at Investigator's discretion)
- (a) UFS-QOL, EQ-5D, and WPAI:SHP Questionnaires
Subjects will be asked to return their completed EQ-5D questionnaire and will be asked to complete the UFS-QOL and WPAI:SHP questionnaires.
- (b) Pregnancy/Pregnancy Outcomes
Subjects will be asked if they have become pregnant since the last follow-up visit. If so, the subject will be released from any remaining protocol specified follow-up assessments and visits, however the subject will be followed and pregnancy outcomes (including any complications) will be recorded as described in Section 10.6 of this protocol.
- (c) Adverse Events

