5.5.2.5 EuroQOL EQ-5D

The EQ-5D should be completed during the subject’s 3rd, 6th, and 12th menstrual cycles post-treatment, preferably on the first full day of bleeding. It should again be completed at 2 years and at 3 years post-treatment. It should be completed based solely on symptoms from that cycle. If the subject has become amenorrheic, the EQ-5D may be completed at any time during the follow-up visit window.

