5.6.4.2 Secondary Efficacy Analysis

There are six secondary endpoints:

- Change in total fibroid volume from Baseline to 12 months
- Change in perfused fibroid volume from Baseline to 12 months
- Change in UFS-QOL from Baseline to 12 months
- OTE at 12 months
- Subject satisfaction at 12 months
- Change in EQ-5D from Baseline to 12 months

Secondary endpoints will be summarized using descriptive statistics.

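### The EQ-5D is tied to the first full day of bleeding at baseline but only preferably so at follow-up, so the single-arm change score could be shifted toward improvement

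*Protocol*

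**What the plan says.** **Baseline.** Protocol 12.1 B says the EQ-5D is "to be completed with consideration to symptoms experienced during the first full day of bleeding during the menstrual cycle" in which the woman completes her PBAC. That is one fixed day in one identified cycle.

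**3, 6 and 12 months.** The Notes on visit materials in protocol 12.3 B place the form in the 3rd, 6th and 12th cycle after treatment. For 12 months the text is "12th menstrual cycle post-treatment, preferably on the first full day of bleeding. It should be completed based solely on symptoms from that cycle"; the Notes for 3 and 6 months have the same construction. The bleeding day is preferred, not required, and the reference for the rating is the cycle. In the 6- and 12-month Notes, if a woman is amenorrheic, "the EQ-5D may be completed at any time during the follow-up visit window". SAP 5.5.2.5 repeats these rules and does not limit the amenorrhea exception to particular visits.

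**Years 2 and 3.** Protocol 12.3 B 5 asks for the form by phone or mail and names no day or cycle. SAP 5.5.2.5 reads "preferably on the first full day of bleeding. It should again be completed at 2 years and at 3 years post-treatment", and its next sentence limits the rating to the symptoms of a cycle without saying which cycle or day applies in those years.

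**Analysis.** SAP 5.6.4.2 lists "Change in EQ-5D from Baseline to 12 months" as a secondary endpoint to be summarized descriptively. SAP 5.6.4 adds that efficacy evaluations are summarized by visit. Neither document plans to record the cycle day that a form describes, or to examine its effect.

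**The concern.** A change score is interpretable only if both ends measure the same thing. Here the baseline is one specified day, while a compliant follow-up form may describe another day or the cycle as a whole. Protocol section 8 makes each woman her own control, so no comparison arm would show the same shift and cancel it.

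The likely direction is toward improvement. The women are enrolled for heavy menstrual bleeding with a PBAC score of at least 150, and the protocol's introduction lists painful periods among fibroid symptoms. The first full day of bleeding is plausibly worse than an average day. If so, forms that move off that day would raise follow-up scores whether or not the device worked.

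The protocol treats the reference period as important elsewhere: Table 2 explains that the WPAI recall was lengthened to 28 days so as to cover a full menstrual cycle. What is at stake is the interpretation of the EQ-5D result. With no test planned, readers will have little beyond the raw mean change.

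**Working it through.** The documents give no EQ-5D effect size, standard deviation or power, so there is no stated figure to reproduce. The check has two parts.

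**1. The instructions side by side**

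| Time point | Day | Cycle | Source |
|---|---|---|---|
| Baseline | First full bleeding day, fixed | The PBAC cycle | Protocol 12.1 B |
| 3 months | Same day, preferred | 3rd after treatment | Protocol 12.3 B 2 Note; SAP 5.5.2.5 |
| 6 months | Same day, preferred | 6th after treatment | Protocol 12.3 B 3 Note; SAP 5.5.2.5 |
| 12 months | Same day, preferred | 12th after treatment | Protocol 12.3 B 4 Note; SAP 5.5.2.5 |
| Years 2 and 3 | None | Protocol: none. SAP: an unnamed cycle | Protocol 12.3 B 5; SAP 5.5.2.5 |

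The day is fixed only at baseline. At 3, 6 and 12 months a form that follows the preference largely matches baseline; one that does not is still compliant.

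**2. Size of the possible shift**

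Suppose treatment has no effect on the EQ-5D. Let f be the share of follow-up forms that do not describe the first full bleeding day. Let d be the mean index for what those forms describe minus the mean index on the first full bleeding day. Then:

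spurious mean change = f × d

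Both f and d are assumptions, because neither is in the documents. Results in index points:

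| | f = 0 | f = 10% | f = 25% | f = 50% | f = 100% |
|---|---|---|---|---|---|
| d = 0 | 0 | 0 | 0 | 0 | 0 |
| d = 0.05 | 0 | 0.005 | 0.0125 | 0.025 | 0.05 |
| d = 0.10 | 0 | 0.01 | 0.025 | 0.05 | 0.10 |
| d = 0.20 | 0 | 0.02 | 0.05 | 0.10 | 0.20 |

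For example, 0.25 × 0.10 = 0.025. The shift is zero if every woman follows the preference (f = 0) or if the days do not differ (d = 0). It favors improvement only if d is above zero. With d = −0.05 and f = 50% it would be −0.025, against the device.

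Amenorrheic women do not belong in f. They have no bleeding day to rate, so their exception is unavoidable and is not in itself a bias.

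**The case against.** The strongest reply is that the plan already points follow-up at the same day. At 3, 6 and 12 months the stated preference is the baseline day, and the EQ-5D is handed out with the PBAC diary and sanitary products, as in the screening kit, so it travels with the bleeding record. A woman who completes it mid-cycle is still told "It should be completed based solely on symptoms from that cycle", and that cycle includes her bleeding days. The day of completion is not necessarily the day rated. The form itself (protocol Appendix A) is not in the text available for review, so its own wording cannot be checked. All of this stands. It limits the likely shift, but it does not make the two references the same: rating a cycle is not rating its first full bleeding day.

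The consequence is also limited. The EQ-5D is one of several descriptive secondary endpoints with no test or success criterion. Protocol section 4 says the 24- and 36-month data are not required for a marketing application, although the by-visit summaries may still show them.

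Two stronger readings are tempting, and the documents support neither.

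- A reader might infer that the EQ-5D change is biased in the device's favor. That requires both departures from the preferred day and milder days on the forms that depart. The documents show neither.
- A reader might infer that years 2 and 3 have no anchor at all, and so treat those forms as ratings of a random calendar day. With the entry criteria of 3–10 bleeding days in a 22–35 day cycle, the non-bleeding share would run from 1 − 10/22 = 0.55 to 1 − 3/35 = 0.91. With d = 0.05–0.10 the shift would be about 0.03–0.09 (0.55 × 0.05 to 0.91 × 0.10). But the SAP does give a cycle reference, though an ambiguous one, and rating a cycle's symptoms is not rating one random day. The figure should not be taken as an estimate.

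**Conclusion.** The mismatch is in the text. The baseline EQ-5D must rate the first full bleeding day of the PBAC cycle. At 3, 6 and 12 months that day is only preferred and the reference is the cycle. At years 2 and 3 the protocol is silent, and the SAP names neither the cycle nor the day. In a single-arm pre-post comparison this could shift the EQ-5D change toward improvement.

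The risk is conditional and its size is unknown. On assumed values of f = 10–50% and d = 0.05–0.10 the shift is 0.005–0.05 index points, and zero remains possible. A direction toward improvement rests on the assumption that the first full bleeding day is worse than the days or cycle described at follow-up. That is plausible in this population but not shown in the documents.

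Study success depends only on the two co-primary endpoints and is unaffected. The 12-month EQ-5D endpoint is where the point matters most. Years 2 and 3 lie outside that endpoint and matter only for the by-visit summaries.

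**What to change.** - **One anchor.** In protocol 12.3 and SAP 5.5.2.5, require at every time point the day used at baseline: the first full day of bleeding, in the PBAC cycle where a PBAC is due. Extend it to years 2 and 3, where the two documents currently differ. Keep the amenorrhea exception. This is practical at 3, 6 and 12 months because the form and the diary are issued together.
- **Record it.** Add a tick-box on the form for whether the answers describe that day.
- **Analysis.** In SAP 5.6.4.2, keep all forms in the main descriptive 12-month summary and add a supportive summary of anchored forms plus amenorrheic women. The main summary should not be restricted to anchored forms. That would select women by what they did after treatment and, if 20–50% of forms were off-anchor, would drop about that share, amenorrheic women aside.
- **Years 2 and 3.** Label any values collected without the anchor as unanchored when they are reported.

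The cost is a small wording change in both documents, one tick-box and one extra summary. The reported EQ-5D gain may turn out smaller.
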